14. APPENDICES

Appendix A. Schedule of Events

Study Activity	Pre-Enrollment	Day 1	Day 2	Day 3	Day 4	Day 5	Day 8	Day 15	Day 29	3 Months	6 Months	12 Months
Eligibility assessment	X											
EKG	X		X ^a									
Pregnancy test (if applicable)	X											
Informed consent	X											
Demographic and baseline variable collection		X										
Randomization		X										
Study drug delivery		X	X	X	X	X						
Assessment for study drug adherence		X	X ^a	X ^a	X ^a	X ^a	X ^b					
Safety monitoring for adverse events		X	X ^a	X ^a	X ^a	X ^a	X ^b	X ^b	X ^b			
Assessment of COVID ordinal outcome score	X		X ^a	X ^a	X ^a	X ^a	X ^b	X ^b	X ^b			
Mortality assessment								X ^b	X ^b			
28-day in-hospital outcomes (chart review)									X			
Long-term outcomes										X ^c	X ^c	X ^c

- a. Assessed only if patient remains hospitalized.
- b. Assessed by telephone follow-up if the patient has been discharged.
- c. Assessed in selected patients in-person, or by telephone or videophone.

Appendix B. Potential medication interactions with hydroxychloroquine

- A. Medications considered contraindicated, which if ordered on an inpatient during the 5-day study period will prompt study personnel to discuss with treating clinicians whether stopping the study drug is appropriate or if this medication cannot be stopped or substituted: amiodarone; chloroquine; cimetidine; dofetilide; phenobarbital; phenytoin; sotalol.

- B. Medications considered to present a potential interaction with hydroxychloroquine, which if ordered on an inpatient during the 5-day study period, will prompt study personnel to discuss with treating clinicians the risk-benefit assessment of this medication and potential need for additional monitoring: ampicillin, antacids, cyclosporine, digoxin, flecainide, mefloquine, methotrexate, mexilitine, rifampicin, rifapentine.

Appendix C: Adverse Event Reporting and Unanticipated Events

As noted in section 11, investigators will report all “serious adverse events,” defined as adverse events that are serious and have a reasonable possibility that the event was due to a study drug or procedure (or of uncertain relatedness), to the CCC within 24 hours. The CCC will then notify the NHLBI and Central Institutional Review Board (cIRB).

The Medical Monitor at the CCC will work collaboratively with the reporting investigator to determine if a serious adverse event has a reasonable possibility of having been caused by the study drug or study procedure, as outlined in 21 CFR 312.32(a)(1), and below. The Medical Monitor will be unblinded and will also determine if the event is unexpected for hydroxychloroquine. An adverse is considered “unexpected” if it is not listed in the investigator brochure or the study protocol (21 CFR 312.32(a)). If a determination is made that a serious adverse event has a reasonable possibility of having been caused by a study procedure or the study drug, it will be classified as a suspected adverse reaction. If the suspected adverse reaction is unexpected, it will be classified as a serious unexpected suspected adverse reaction (SUSAR).

The CCC will report all unexpected deaths, serious and treatment related adverse events, and SUSARs to the DSMB, NHLBI, and cIRB within 7 days after receipt of the report from a clinical site. A written report will be sent to the NHLBI, DSMB, FDA, and the cIRB within 15 calendar days. The DSMB will also review all reported adverse events and clinical outcomes during scheduled interim analyses. The CCC will distribute the written summary of the DSMB’s periodic review of reported adverse events to the cIRB in accordance with NIH guidelines (<http://grants.nih.gov/grants/guide/notice-files/not99-107.html>). The Medical Monitor will provide to Sandoz Pharmacovigilance any significant safety findings (without disclosing protected health information) during the conduct of the trial.

C.1. Unanticipated Problems (UP)

Investigators must also report Unanticipated Problems, regardless of severity, associated with study procedures within 24 hours. An unanticipated problem is defined as follows: any incident, experience, or outcome that meets all of the following criteria:

- Unexpected, in terms of nature, severity, or frequency, given the research procedures that are described in the protocol-related documents, such as the IRB-approved research protocol and informed consent document; and the characteristics of the subject population being studied;
- Related or possibly related to participation in the research, in this guidance document, possibly related means there is a reasonable possibility that the incident, experience, or outcome may have been caused by the procedures involved in the research;
- Suggests that the research places subjects or others at a greater risk of harm (including physical, psychological, economic, or social harm) than was previously known or recognized.

C.2. Determining Relationship of Adverse Events to Study Drug or Study Procedures

Investigators will be asked to grade the strength of the relationship of an adverse event to study drug or study procedures as follows:

- **Definitely Related:** The event follows: a) A reasonable, temporal sequence from a study procedure; and b) Cannot be explained by the known characteristics of the patient’s clinical state or other therapies; and c) Evaluation of the patient’s clinical state indicates to the investigator that the experience is definitely related to study procedures.
- **Probably or Possibly Related:** The event should be assessed following the same criteria for “Definitely Associated”. If in the investigator’s opinion at least one or more of the criteria are not present, then “probably” or “possibly” associated should be selected.
- **Probably Not Related:** The event occurred while the patient was on the study but can reasonably be explained by the known characteristics of the patient’s clinical state or other therapies.
- **Definitely Not Related:** The event is definitely produced by the patient’s clinical state or by other modes of therapy administered to the patient.
- **Uncertain Relationship:** The event does not meet any of the criteria previously outlined.

[figure not shown]
C.3. Clinical Outcomes that may be Exempt from Adverse Event Reporting

Study-specific outcomes of acute respiratory infection, COVID-19, and critical illness will be systematically collected for all patients in both study group and are exempt from adverse event reporting unless the investigator considers the event to be Definitely or Possibly Related (or of an Uncertain Relationship) to the study drug or study procedures. Examples of study-specific clinical outcomes include:

- Death not related to the study procedures
- Neurological events
 - Seizure
- Cardiovascular events
 - Receipt of vasopressors
 - Atrial or ventricular arrhythmia
 - Cardiac arrest
- Respiratory events
 - Hypoxemia requiring supplemental oxygen
 - Acute respiratory distress syndrome
 - Receipt of mechanical ventilation
 - Receipt of extra-corporeal membrane oxygenation
- Gastrointestinal events
 - Elevation of aspartate aminotransferase or alanine aminotransferase
 - Acute pancreatitis
- Renal events
 - Acute kidney injury
 - Receipt of renal replacement therapy
- Endocrine events
 - Symptomatic hypoglycemia
- Hematologic or coagulation events
 - Neutropenia, lymphopenia, anemia, or thrombocytopenia
- Dermatologic events
 - Severe dermatologic reaction (e.g., Steven’s Johnson Syndrome)

Note: A study-specific clinical outcome may also qualify as a reportable adverse event. For example, a ventricular arrhythmia that the investigator considers Definitely or Possibly Related to the study drug would be both recorded as a study-specific clinical outcome and reported as a Serious and Definitely or Possibly Related Adverse Event.

C.4. Decision tree for determining if an adverse event is reportable

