11.2 Safety Monitoring

Assuring patient safety is an essential component of this protocol. Each participating investigator has primary responsibility for the safety of the individual participants under his or her care. The Investigators will determine daily if any adverse events occur during the period from enrollment through **study day 7** (48 hours after completion of the study drug) or hospital discharge, whichever occurs first and will determine if such adverse events are reportable. Thereafter, adverse events are not required to be reported unless the investigator feels the adverse event was related to study drug or study procedures.

The following adverse events will be considered reportable and thus collected in the adverse event case report forms:

- Serious adverse events
- Non-serious adverse events that are considered by the investigator to be related to study procedures or of uncertain relationship (Appendix C)
- Events leading to permanent discontinuation of study drug

Study-specific clinical outcomes (Primary, Secondary and Safety Outcomes and Assessments During the Study), including serious outcomes such as organ failures and death, are systematically recorded in the case report forms and are exempt from adverse event reporting unless the investigator deems the event to be related to the administration of study drug or the conduct of study procedures (or of uncertain relationship) as outlined in Appendix C.

After randomization, adverse events must be evaluated by the investigator. If the adverse event is judged to be reportable, as outlined above, then the investigator will report to the CCC their assessment of the potential relatedness of each adverse event to the study drug or protocol procedure via electronic data entry. Investigators will assess if there is a reasonable possibility that the study procedure caused the event, based on the criteria outlined in Appendix C. Investigators will also consider if the event is unexpected. Unexpected adverse events are events not listed in the study protocol and the investigator brochure for Hydroxychloroquine. Investigators will also determine if adverse events are unanticipated given the patient's clinical course, previous medical conditions, and concomitant medications.

If a patient's treatment is discontinued as a result of an adverse event, study site personnel must also report the circumstances and data leading to discontinuation of treatment in the adverse event case report forms.

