11.3 Serious Adverse Events

Serious adverse event collection begins after randomization and study procedures have been initiated. If a patient experiences a serious adverse event after consent, but prior to randomization or starting study procedures, the event will NOT be collected. Study site personnel must alert the CCC of any **serious and**

study procedure related adverse event within 24 hours of investigator awareness of the event. Alerts issued via telephone are to be immediately followed with official notification on the adverse event case report form. See Appendix C for reporting timelines for serious, unexpected, study related events (SAEs) and serious, unexpected suspected adverse reactions (SUSARs)

As per the FDA and NIH definitions, a serious adverse event is any adverse event that results in one of the following outcomes:

- Death
- A life-threatening experience (that is, immediate risk of dying)
- Prolonged inpatient hospitalization or re-hospitalization

As per <http://www.fda.gov/Safety/MedWatch/HowToReport/ucm053087.htm>: Report if admission to the hospital or prolongation of hospitalization was a result of the adverse event. Emergency room visits that do not result in admission to the hospital should be evaluated for one of the other serious outcomes (e.g., life-threatening; required intervention to prevent permanent impairment or damage; other serious medically important event).

- Persistent or significant disability/incapacity

As per <http://www.fda.gov/Safety/MedWatch/HowToReport/ucm053087.htm>: Report if the adverse event resulted in a substantial disruption of a person's ability to conduct normal life functions, i.e., the adverse event resulted in a significant, persistent or permanent change, impairment, damage or disruption in the patient's body function/structure, physical activities and/or quality of life.

Reportable serious adverse events that may not result in death, be life-threatening, or require hospitalization may be considered serious adverse events when, based upon appropriate medical judgment, they may jeopardize the patient and may require medical or surgical intervention to prevent one of the outcomes listed in this definition.

Serious adverse events will be collected during the first **7 study days** or until hospital discharge, whichever occurs first, regardless of the investigator's opinion of causation.

12. Data and Safety Monitoring Board (DSMB)

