7.6 Presentation of Adverse Events

The frequency and description of adverse events will be reported for all enrolled patients and by randomized group (hydroxychloroquine vs placebo).

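### An unblinded Medical Monitor shares the causality decision on reported serious adverse events, so by-arm counts of related SAEs and SUSARs can reflect knowledge of allocation

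*Protocol*

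**What the plan says.** Protocol Appendix C makes causality a joint decision: "The Medical Monitor at the CCC will work collaboratively with the reporting investigator to determine if a serious adverse event has a reasonable possibility" of a causal link to study drug or procedure. It continues: "The Medical Monitor will be unblinded and will also determine if the event is unexpected for hydroxychloroquine". An event judged possibly caused by drug or procedure becomes a suspected adverse reaction and, if also unexpected, a SUSAR. The coordinating center sends unexpected deaths, serious treatment-related events and SUSARs to the DSMB, NHLBI and the central IRB within 7 days.

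Protocol section 11.2 describes the step before this. The investigator judges whether an event is reportable and enters a relatedness assessment electronically. Section 3.7 keeps participants, treating clinicians, study personnel and outcome assessors blinded and names no exception for this exchange. Section 12 has the Medical Monitor help prepare the DSMB reports and allows the Monitor to review unblinded data.

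The documents describe SAEs in two ways. Section 11.3 collects them for the first 7 study days or until discharge, "whichever occurs first, regardless of the investigator's opinion of causation". Appendix C, citing section 11, uses the same term for a narrower set, "defined as adverse events that are serious and have a reasonable possibility that the event was due to a study drug or procedure". That set also takes in events whose relatedness is unclear.

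**The concern.** Unblinding someone centrally to judge expectedness is ordinary practice. Here the same unblinded person also takes part in the causality judgment. The grades in Appendix C.2 turn on whether the patient's clinical state or other therapies explain the event, which is a matter of opinion in acutely ill patients with COVID-19. Anyone who knows the patient received placebo has a reason, unrelated to the clinical facts, to call the event unrelated to drug. If that opinion enters the shared decision, related SAEs and SUSARs could differ between arms even when the underlying event rates are equal.

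The DSMB would see these subsets as a safety signal. The discussion could also let the site infer the arm. Section 4.6 controls unblinding after clinical deterioration: the site asks the coordinating center and records the reason. The Appendix C exchange has no comparable control.

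**Working it through.** The plan attaches no figure to this procedure, so there is nothing to reproduce. The check is which counts the Monitor's judgment can reach.

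**1. Who decides whether an event is reported?** In each rule it is the blinded investigator.
- Section 11.2 makes reportable "Non-serious adverse events that are considered by the investigator to be related to study procedures or of uncertain relationship". Events leading to permanent discontinuation of study drug are reportable in any case.
- Events after study day 7 or discharge need reporting only if the investigator considers them related (section 11.2).
- Under Appendix C.3, study-specific outcomes "are exempt from adverse event reporting unless the investigator considers the event to be Definitely or Possibly Related" or of uncertain relationship.

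The Monitor works with the *reporting* investigator, so the event has already been reported. The Monitor's direct effect is on classification.

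**2. Which counts depend on that classification?**

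| Count | Open to the Monitor's causality judgment? |
|---|---|
| Related SAEs, suspected adverse reactions, SUSARs (Appendix C) | Yes, directly |
| All SAEs to day 7 or discharge (11.2, 11.3) | No; collected whatever the cause. Exempt outcomes are captured separately |
| Non-serious events, late events, exempt outcomes reported as adverse events | Only indirectly, if the arm leaks to the investigator |
| Safety outcomes (SAP 7.5, Appendices A and B) | No; collected in both arms to Study Day 29 with no relatedness filter |
| 14- and 28-day all-cause mortality | No |
| Day 15 ordinal scale | No direct route |

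**3. Is there a safeguard in the visible text?** Section 11.2 puts the investigator's recorded rating before the Monitor's step, but does not say that it is final. Section 3.7 states the blinding rule in general terms. No visible sentence locks the rating or forbids disclosure of the arm during the joint review. The decision tree in Appendix C.4 is a figure that could not be seen, so this finding is limited to the text.

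**4. Illustration on assumed rates.** Planned enrollment is 510 at 1:1, or 510 / 2 = 255 per arm (Protocol 7.1, SAP 4.3). Assume a true rate *p* of reported SAEs, equal in both arms, of which a fraction *q* is called related. Knowledge of the arm moves that fraction to *q* + *s* on hydroxychloroquine and *q* − *s* on placebo.

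- Expected related count = 255 × *p* × (*q* ± *s*).
- With *p* = 0.10, *q* = 0.30, *s* = 0: 255 × 0.030 = 7.65 in each arm; odds ratio 1.0.
- With *s* = 0.05: 255 × 0.035 = 8.9 against 255 × 0.025 = 6.4. Odds ratio = (0.035/0.965) / (0.025/0.975) = 1.41.
- With *s* = 0.10: 255 × 0.040 = 10.2 against 255 × 0.020 = 5.1. Odds ratio = (0.040/0.960) / (0.020/0.980) = 2.04.
- Over *p* from 0.05 to 0.20, *q* from 0.20 to 0.50 and *s* from 0.05 to 0.10, the odds ratio runs from 1.23 (*p* = 0.05, *q* = 0.50, *s* = 0.05) to 3.13 (*p* = 0.20, *q* = 0.20, *s* = 0.10).

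The total of SAEs collected regardless of causality stays at 255 × *p* in each arm, so its odds ratio is 1.0 throughout.

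**The case against.** The strongest reply is that reporting and classification are separate steps and that the main safety evidence lies elsewhere. A blinded investigator applies every reporting filter. Arrhythmia, seizure, cardiac arrest and the other listed safety outcomes are recorded for everyone and compared by arm with simple logistic regression. Appendix C also has the DSMB review all reported adverse events and clinical outcomes, so it does not depend on the related subset. All of this stands, and it confines the problem to that subset and to possible leakage.

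A reader might infer that adverse event counts by arm are biased in general, because SAP 7.6 states: "The frequency and description of adverse events will be reported for all enrolled patients and by randomized group". The documents do not support that. SAP 7.6 is descriptive and does not mention relatedness, and SAEs to day 7 or discharge are collected whatever the cause. A wider effect would need the arm to leak, or sites to apply the narrower SAE definition in Appendix C as a filter on what they report. The second is possible on the wording. However, section 11.3 also has a 24-hour alert for serious related events, and Appendix C may have meant only that.

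A reader might also infer a threat to the primary outcome, since level 6 versus level 7 rests on reported usual activities. That requires the arm to leak in an SAE discussion, reach the telephone assessor or the patient, and change an answer about usual activities. No passage describes this, and section 3.7 requires outcome assessors to stay blinded.

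**Conclusion.** The point holds in a limited form. An unblinded Monitor takes part in the causality decision, and no visible text protects the investigator's blinded rating or bars disclosure of the arm. By-arm counts of related SAEs and SUSARs, including those the DSMB sees, can therefore reflect allocation, and leakage to the site is possible.

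The size cannot be derived from the documents. The odds ratios of about 1.2 to 3.1 show what the assumed attribution shifts would do to a small subset count. They are not evidence that such shifts would occur. The conclusion assumes that the Monitor knows the individual patient's arm when causality is discussed, which is the plain reading of Appendix C, and that the unseen decision tree in C.4 adds no lock. The efficacy analysis and the main safety comparison stand as planned. This is a cheap improvement, not a flaw that threatens the trial's conclusions.

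**What to change.** Amend Protocol Appendix C as follows.

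1. Treat the investigator's blinded causality rating, already entered electronically under section 11.2, as final and locked before any discussion with the Monitor.
2. Keep the Monitor's unblinded judgment as a separate record, used only for expectedness, SUSAR classification and expedited reporting.
3. State that allocation is not disclosed to the site in this exchange, and name the Monitor as an exception in section 3.7.
4. Base any by-arm count of related events on the locked blinded rating, and say so in SAP 7.6.
5. Reconcile the meaning of serious adverse event in Appendix C with sections 11.2 and 11.3, for example by giving the 24-hour set of related or uncertain events its own name.

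Asking the Monitor to rate causality while blinded would be less reliable, because section 12 already gives the Monitor possible access to unblinded data for the DSMB reports.

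The cost is a wording change with the same staff and timelines. The downside is two causality records that may disagree. The DSMB would need to know which one each count uses.

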Appendix D. Public Readiness and Emergency Preparedness Act

This study is being conducted to determine whether hydroxychloroquine can safely and effectively be used to mitigate, treat, or cure COVID-19 or limit the harm of the COVID-19 pandemic in accordance with the Secretary of the Department of Health and Human Services' (HHS's) Declaration under the Public Readiness and Emergency Preparedness Act for medical countermeasures against COVID-19 (COVID-19 Declaration) effective February 4, 2020. The purpose of this study is to test if hydroxychloroquine results in clinical benefit in patients hospitalized with COVID- 19.

Hydroxychloroquine has been approved by the FDA for other uses and its investigational use for COVID-19 in this study has been exempted by the FDA from investigational new drug application requirements pursuant to 21 CFR 312.2(b)(1). This study is conducted under a Research Project Cooperative Agreement with the National Heart, Lung, and Blood Institute.

Appendix E: ORCHID-BUD Ancillary Study Protocol

1. **Title:** Outcomes Related to COVID-19 treated with Hydroxychloroquine among In-patients with symptomatic Disease – Brain Outcomes and Psychological Distress (ORCHID-BUD)
2. **Objective:**
 - **Aim 1:** To determine (a) the epidemiology (i.e., prevalence) of cognitive impairment (i.e., acquired-Alzheimer’s Disease and Related Dementia [ADRD]) characterized by impairments in memory, attention, language, reasoning, and executive function at 12-months in adults hospitalized with COVID-19 infection, and (b) if hydroxychloroquine administration is associated with improvement in these same outcomes.
 - **Aim 2:** To determine (a) the epidemiology of post-traumatic stress disorder (PTSD) and depression at 12-months in adults who are hospitalized with COVID-19 infection, and (b) if hydroxychloroquine administration is associated with improvement in these same outcomes.
 - **Aim 3:** To identify modifiable risk factors (e.g., sedatives, isolation, intravenous fluids, antibiotics, pressor, angiotensin-converting enzyme [ACE]-inhibitor or angiotensin II receptor blocker [ARB] use, etc.) associated with worse long-term cognitive impairment, PTSD, and depression at 12 months in adults hospitalized with COVID-19 infection.
3. **Hypothesis:** The primary hypothesis of this proposal is that (a) COVID-19 survivors will have a high burden of ADRD, PTSD, and depression. The secondary hypothesis is that hydroxychloroquine will lower the burden of these three outcomes as compared to placebo.
4. **Study Design:** ORCHID-BUD will assess 12-month cognition, PTSD, and depression using a comprehensive phone battery in all patients enrolled in ORCHID since the beginning of the study (March 2020). ORCHID-BUD essentially expands and better defines the ORCHID’s follow-up study procedures that are already described its study protocol (ORCHID protocol Version 1.1, Section 6.3.2, and page 22):“We will follow-up selected patients at 3, 6, and 12 months to assess vital status, cognition, basic and instrumental activities of daily living, quality of life, employment status, physical disability, and psychological distress (i.e., depression, post-traumatic stress disorder, etc.), place of residence, and rehospitalizations. These assessments may occur by phone, in-person, or videoconferencing.” In anticipation of ORCHID-BUD, the ORCHID parent study has already added language to the informed consent document to conduct the proposed study procedures, including the baseline phone interview with the patient and family member:

Study Procedure 6: Follow-up Phone Calls	
Timing	Around Day 7, Day 15, and Day 28 if you have been discharged from the hospital before those times. Long-term Follow-up 3, 6, and 12 months
Explanation	A study team member will call you and/or a family member for follow-up information about how you are doing and if you have had any problems that might be due to the study medication. We may also contact you at 3, 6, and 12 months to see how you are doing. We may ask you do some tasks to see how your brain is working. For example, we may ask you to repeat a list of numbers or name many words that start with the letter “P”. We may also ask you questions about your health, ability to do common daily activities, employment status, quality of life, and how you are feeling. These assessments may be done over the phone, in-person, or videoconferencing. We will confidentially and securely collect your medical record number and personal information, so we can stay in contact with you.
Risks or Discomforts	You may find the phone calls and questions inconvenient.

Therefore, the ORCHID-BUD study activities will be considered part of the ORCHID parent study activities, and separate informed consent will not be performed.

5. Study procedures:

